2.4.4.4 Multiplicity issues

To control the type-I error rate for the analysis of efficacy endpoint, a hierarchical testing procedure will be applied at a 2-sided 5% significant level, ie, each hypothesis will be formally tested only if the preceding one is significant at the 2-sided 5% level.

To match the approved indication in adults and adolescents, for the US and US reference countries, the testing hierarchy will start with baseline blood eosinophils ≥ 0.3 Giga/L population. For EU and EU reference countries, the testing hierarchy will start with Type 2 inflammatory asthma phenotype population. The complete list of the endpoints with their testing order is specified in [Table 9](#) (For US and US reference countries) and [Table 10](#) (for EU and EU reference countries).

For US and US reference countries:

Table 9 - Hierarchical testing order for US and US reference countries:

Endpoints	Population	Test Order
Annualized rate of severe exacerbation events during the 52-week placebo-controlled treatment period	Patients with baseline blood eosinophils ≥ 0.3 Giga/L	1 st
Annualized rate of severe exacerbation events during the 52-week placebo-controlled treatment period	Patients with baseline blood eosinophils ≥ 0.15 Giga/L	2 nd
Annualized rate of severe exacerbation events during the 52-week placebo-controlled treatment period	Type 2 inflammatory asthma phenotype (Baseline blood eosinophils ≥ 0.15 Giga/L or Baseline FeNO ≥ 20 ppb)	3 rd
Change from baseline in pre-bronchodilator % predicted FEV1 at Week 12.	Patients with baseline blood eosinophils ≥ 0.3 Giga/L	4 th
Change from baseline in pre-bronchodilator % predicted FEV1 at Week 12.	Patients with baseline blood eosinophils ≥ 0.15 Giga/L	5 th
Change from baseline in pre-bronchodilator % predicted FEV1 at Week 12.	Type 2 inflammatory asthma phenotype (Baseline blood eosinophils ≥ 0.15 Giga/L or Baseline FeNO ≥ 20 ppb)	6 th
Change in ACQ-7-IA at Week 24	Patients with baseline blood eosinophils ≥ 0.3 Giga/L	7 th
Change in ACQ-7-IA at Week 24	Patients with baseline blood eosinophils ≥ 0.15 Giga/L	8 th
Change in ACQ-7-IA at Week 24	Type 2 inflammatory asthma phenotype (Baseline blood eosinophils ≥ 0.15 Giga/L or Baseline FeNO ≥ 20 ppb)	9 th
Annualized rate of severe exacerbation events during the 52-week placebo-controlled treatment period	Baseline FeNO ≥ 20 ppb	10 th
Change from baseline in pre-bronchodilator % predicted FEV1 at Week 12	Baseline FeNO ≥ 20 ppb	11 th
Change in ACQ-7-IA at Week 24	Baseline FeNO ≥ 20 ppb	12 th

Annualized rate of severe exacerbation events during the 52-week placebo-controlled treatment period	Full ITT	13 th
Change from baseline in pre-bronchodilator % predicted FEV1 at Week 12.	Full ITT	14 th
Annualized rate of severe exacerbation events during the 52-week placebo-controlled treatment period	Patients with baseline blood eosinophils ≥ 0.3 Giga/L and High ICS at baseline	15 th
Annualized rate of severe exacerbation events during the 52-week placebo-controlled treatment period	Patients with baseline blood eosinophils ≥ 0.15 Giga/L and High ICS at baseline	16 th
Annualized rate of severe exacerbation events during the 52-week placebo-controlled treatment period	Type 2 inflammatory asthma phenotype (Baseline blood eosinophils ≥ 0.15 Giga/L or Baseline FeNO ≥ 20 ppb) with High ICS at baseline	17 th
Annualized rate of severe exacerbation events during the 52-week placebo-controlled treatment period	Baseline FeNO ≥ 20 ppb with High ICS at baseline	18 th
Annualized rate of severe exacerbation events during the 52-week placebo-controlled treatment period	Full ITT with High ICS at baseline	19 th
Change from baseline in FeNO at Week 12	Patients with baseline blood eosinophils ≥ 0.3 Giga/L	20 th
Change from baseline in FeNO at Week 12	Patients with baseline blood eosinophils ≥ 0.15 Giga/L	21 st
Change from baseline in FeNO at Week 12	Type 2 inflammatory asthma phenotype (Baseline blood eosinophils ≥ 0.15 Giga/L or Baseline FeNO ≥ 20 ppb)	22 nd
Change from baseline in FeNO at Week 12	Baseline FeNO ≥ 20 ppb	23 rd
Change from baseline in FeNO at Week 12	Full ITT	24 th

For EU and EU reference countries:

Table 10 - Hierarchical testing order for EU and EU reference countries

Endpoints	Population	Test Order
Annualized rate of severe exacerbation events during the 52-week placebo-controlled treatment period	Type 2 inflammatory asthma phenotype (Baseline blood eosinophils ≥ 0.15 Giga/L or Baseline FeNO ≥ 20 ppb)	1 st
Annualized rate of severe exacerbation events during the 52-week placebo-controlled treatment period	Patients with baseline blood eosinophils ≥ 0.15 Giga/L	2 nd
Annualized rate of severe exacerbation events during the 52-week placebo-controlled treatment period	Patients with baseline blood eosinophils ≥ 0.3 Giga/L	3 rd
Change from baseline in pre-bronchodilator % predicted FEV1 at Week 12.	Type 2 inflammatory asthma phenotype (Baseline blood eosinophils ≥ 0.15 Giga/L or Baseline FeNO ≥ 20 ppb)	4 th

Change from baseline in pre-bronchodilator % predicted FEV1 at Week 12.	Patients with baseline blood eosinophils ≥ 0.15 Giga/L	5 th
Change from baseline in pre-bronchodilator % predicted FEV1 at Week 12.	Patients with baseline blood eosinophils ≥ 0.3 Giga/L	6 th
Change in ACQ-7-IA at Week 24	Type 2 inflammatory asthma phenotype (Baseline blood eosinophils ≥ 0.15 Giga/L or Baseline FeNO ≥ 20 ppb)	7 th
Change in ACQ-7-IA at Week 24	Patients with baseline blood eosinophils ≥ 0.15 Giga/L	8 th
Change in ACQ-7-IA at Week 24	Patients with baseline blood eosinophils ≥ 0.3 Giga/L	9 th
Annualized rate of severe exacerbation events during the 52-week placebo-controlled treatment period	Baseline FeNO ≥ 20 ppb	10 th
Change from baseline in pre-bronchodilator % predicted FEV1 at Week 12	Baseline FeNO ≥ 20 ppb	11 th
Change in ACQ-7-IA at Week 24	Baseline FeNO ≥ 20 ppb	12 th
Annualized rate of severe exacerbation events during the 52-week placebo-controlled treatment period	Full ITT	13 th
Change from baseline in pre-bronchodilator % predicted FEV1 at Week 12.	Full ITT	14 th
Annualized rate of severe exacerbation events during the 52-week placebo-controlled treatment period	Type 2 inflammatory asthma phenotype (Baseline blood eosinophils ≥ 0.15 Giga/L or Baseline FeNO ≥ 20 ppb) with High ICS at baseline	15 th
Annualized rate of severe exacerbation events during the 52-week placebo-controlled treatment period	Patients with baseline blood eosinophils ≥ 0.15 Giga/L and High ICS at baseline	16 th
Annualized rate of severe exacerbation events during the 52-week placebo-controlled treatment period	Patients with baseline blood eosinophils ≥ 0.3 Giga/L and High ICS at baseline	17 th
Annualized rate of severe exacerbation events during the 52-week placebo-controlled treatment period	Baseline FeNO ≥ 20 ppb and High ICS at baseline	18 th
Annualized rate of severe exacerbation events during the 52-week placebo-controlled treatment period	Full ITT and High ICS at baseline	19 th
Change from baseline in FeNO at Week 12	Type 2 inflammatory asthma phenotype (Baseline blood eosinophils ≥ 0.15 Giga/L or Baseline FeNO ≥ 20 ppb)	20 th
Change from baseline in FeNO at Week 12	Patients with baseline blood eosinophils ≥ 0.15 Giga/L	21 st
Change from baseline in FeNO at Week 12	Patients with baseline blood eosinophils ≥ 0.3 Giga/L	22 nd
Change from baseline in FeNO at Week 12	Baseline FeNO ≥ 20 ppb	23 rd
Change from baseline in FeNO at Week 12	Full ITT	24 th

2.4.4.5 Additional efficacy analysis(es)

2.4.4.5.1 Analysis of additional PROs

Change from baseline in additional PRO endpoints listed in [Section 2.1.3.5](#) will be analyzed using the same MMRM model for the key secondary endpoint analysis as described in [Section 2.4.4.2.1](#) in the Type 2 inflammatory asthma phenotype and baseline blood eosinophils ≥ 0.3 Giga/L populations defined in [Section 2.3.1](#). Differences in LS means, the corresponding 95% CI and the p-value will be provided for comparison between dupilumab and placebo along with descriptive statistics.

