11.4.4.3 Pharmacodynamics and Phenotyping

The values to be used as baselines will be those collected at Visit 2 (Day 1). If any of the scheduled assessments on Day 1 are technically disqualified (eg, insufficient sample), then values determined in any other samples collected prior to the first IMP administration can be used as baseline.

For all parameters, raw data, absolute changes from baseline and percent changes from baseline will be summarized in descriptive statistics by treatment group and time point.

Summary plots (mean \pm SEM) on raw data, absolute changes from baseline and percent changes from baseline will be provided by treatment group.

As part of exploratory analysis, correlations between the baseline values for biomarkers and efficacy endpoints will be assessed.

11.4.5 Analyses of Patient Reported Outcomes (Health-related Quality of Life/Health Economics Variables)

Patient reported outcome variables collected in this study include the ACQ-IA questionnaire ACQ-7 score, PAQLQ(S)-IA score, PACQLQ score, and PRQLQ-IA score (in those with history of allergic rhinitis). The change from baseline for these endpoints will be analyzed using MMRM in the same fashion as for the endpoint of pre-bronchodilator % predicted FEV1. The covariates to be included are treatment, age, weight ($\leq 30\text{kg}$, $>30\text{kg}$), region, baseline eosinophil level ($<300\text{ cells}/\mu\text{L}$, $\geq 300\text{ cells}/\mu\text{L}$), baseline FeNO level ($<20\text{ ppb}$, $\geq 20\text{ ppb}$), baseline ICS dose level (medium/high), visit, treatment-by-visit interaction, corresponding baseline value and baseline-by-visit interaction. Descriptive statistics including number of patients, mean, standard error and LS means will be provided for each timepoint. In addition, differences in LS means, the corresponding 95% CI and the p-value will be derived from the MMRM model for comparison of dupilumab against placebo at each timepoint. Note that PRQLQ-IA score (in those with history of allergic rhinitis) will only be analyzed for patients with the history of allergic rhinitis.

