2.0	Current version	When performing the key secondary endpoint analysis in the Type 2 inflammatory asthma phenotype, baseline blood eosinophils ≥0.15 Giga/L, and full ITT populations, the model will include change from baseline in % predicted FEV1 values up to Week 12 as response variables, and treatment, age, baseline weight, region, sex, ethnicity, baseline height, baseline eosinophil level, baseline FeNO level, baseline ICS dose level, visit, treatment by-visit interaction, baseline % predicted FEV1 value and baseline-by-visit interaction as covariates.	
The model covariates are updated by removing age, sex, and baseline height:
 
When performing the key secondary endpoint analysis in the Type 2 inflammatory asthma phenotype, baseline blood eosinophils ≥0.15 Giga/L, and full ITT populations, the model will include change from baseline in % predicted FEV1 values up to Week 12 as response variables, and treatment, baseline weight, region, ethnicity, baseline eosinophil level, baseline FeNO level, baseline ICS dose level, visit, treatment by-visit interaction, baseline % predicted FEV1 value and baseline-by-visit interaction as covariates.
	The effect of age, sex, and height on the predicted FEV1 have already been accounted in the predicted FEV1 calculation equation.

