2.1.3.5.5 Euro Qol (EQ-5D-Y) – for Children

The EQ-5D-Y will be completed by children (relates to the quality of life to the child). Those who can read are encouraged to fill the questionnaire by themselves. Those who cannot read, fill it with the help of their adult caregiver (parent/caregiver).

The EQ-5D-Y consists of 2 pages, the EQ-5D-Y descriptive system and the EQ visual analogue scale (VAS; see [Appendix H](#)). The descriptive system assesses 5 dimensions but using a child-friendly wording (mobility, looking after myself, doing usual activities, having pain or discomfort, feeling worried, sad or unhappy). Each dimension has 3 levels: no problems, some problems, a lot of problems. The respondent is asked to indicate his/her health state by ticking (or placing a cross) in the box against the most appropriate statement in each of the 5 dimensions. The EQ VAS records the respondent's self-rated health on a vertical, visual analogue scale where the endpoints are labelled 'The best health you can imagine' and 'The worst health you can imagine'. This information can be used as a quantitative measure of health outcome as judged by the individual respondents. Also, previously published studies by EuroQol Group members showed preliminary evidence of the instrument's feasibility, reliability and validity.

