2.4.4.2 Analyses of key secondary efficacy endpoints

Statistical analysis methods for the key secondary endpoints are presented below.

2.4.4.2.1 Change from baseline in percentage predicted pre-bronchodilator (pre-BD) FEV₁ at Week 12

Primary statistical model and adjustment for covariates

The analysis of change from baseline in % predicted pre-BD FEV₁ at Week 12 is to assess the efficacy of dupilumab regardless of treatment adherence. The absolute change from baseline in % predicted FEV₁ at Week 12 will be analyzed using a mixed-effect model with repeated measures (MMRM) approach. The analysis for change from baseline in % predicted pre-BD FEV₁ will be performed in the Type 2 inflammatory asthma phenotype, baseline blood eosinophils ≥ 0.3 Giga/L, baseline blood eosinophils ≥ 0.15 Giga/L, baseline FeNO ≥ 20 ppb and full ITT populations.

When performing the key secondary endpoint analysis in the Type 2 inflammatory asthma phenotype, baseline blood eosinophils ≥ 0.15 Giga/L, and full ITT populations, the model will include change from baseline in % predicted FEV₁ values up to Week 12 as response variables, and treatment, baseline weight, region, ethnicity, baseline eosinophil level, baseline FeNO level, baseline ICS dose level, visit, treatment by-visit interaction, baseline % predicted FEV₁ value and baseline-by-visit interaction as covariates. When performing the key secondary endpoint analysis in the baseline blood eosinophils ≥ 0.3 Giga/L population, the baseline eosinophil level will be removed from the model covariates. When performing the key secondary endpoint analysis in the baseline FeNO ≥ 20 ppb population, the baseline FeNO level will be removed from the model covariates.

Treatment group, baseline weight, region, baseline eosinophil level, baseline FeNO level, ethnicity, baseline ICS dose level, and visit will be treated as categorical variables. For patients who discontinue the treatment before Week 12, they will be asked and encouraged to return to the clinic for all remaining study visit and the additional off-treatment % predicted FEV₁ values measured up to Week 12 will be included in the primary analysis. For patients who withdraw from the study before Week 12, % predicted FEV₁ values will be missing after study discontinuation. No imputation will be performed for missing values in the primary analysis. This estimand

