compares the change from baseline in % predicted pre-BD FEV1 for the patients randomized to the dupilumab and placebo arms, regardless of what treatment patients actually received. It assesses the benefits of the treatment policy or strategy relative to placebo.

An unstructured correlation matrix will be used to model the within-patient errors. Parameters will be estimated using restricted maximum likelihood method with the Newton-Raphson algorithm. Statistical inferences on treatment comparisons for the change from baseline in % predicted FEV1 at Week 12 will be derived from the mixed-effect model. Difference in LS mean change from baseline, the corresponding 95% CI and the p-value with Kenward-Roger adjustment will be provided for comparison for dupilumab against placebo. In addition, descriptive statistics including number of patients, mean, standard error and LS mean of change from baseline will be provided.

A sample SAS code can be found below:

```
proc mixed data=adsd.adre method=reml;

    where paramcd='FEV1PP' and ATPT='PRE-BRONCHODILATOR' and avisitn ge 3 and
    avisitn le 8 and ittfl='Y';

    class subjid weight eosblgpn1 fenoblgn1 ics trt01pn avisitn cntygr1n ethnicity;

    model chg = trt01pn weight ics eosblgpn1 fenoblgn1 cntygr1n ethnicity avisitn
    trt01pn*avisitn base base*avisitn/ddfm=kr residual;

    repeated avisitn/type=un subject=subjid;

    lsmeans trt01pn*avisitn /pdiff cl;

    estimate 'dupilumab vs Placebo at Week 12 Visit 8'

    trt01pn -1 1 trt01pn*avisitn 0 0 0 0 0 -1 0 0 0 0 0 1/cl;

run;
```

The primary estimand for the key secondary endpoint is summarized as in below [Table 7](#).

Table 7 - Summary of primary estimand for key secondary endpoint

Endpoint Category (estimand)	Estimands			
	Endpoint	Population	Intercurrent event(s) strategy and missing data handling	Population-level summary
Primary objective: The primary objective is to evaluate the efficacy of dupilumab in children 6 to <12 years of age with uncontrolled persistent asthma				

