In the Type 2 inflammatory asthma phenotype and baseline blood eosinophils ≥ 0.3 Giga/L populations, change from baseline for other continuous endpoints at all time-points will be analyzed using MMRM model including measurements up to Week 52. The model will include change from baseline of these endpoints from all available planned time points up to Week 52 as response variables, regardless if the patient is on treatment or not when the endpoint is measured. When performing these analyses in the Type 2 inflammatory asthma phenotype population, treatment, age, baseline weight, region (pooled country), baseline eosinophil level, baseline FeNO level, baseline ICS dose level, visit, treatment by-visit interaction, baseline endpoint value and baseline-by-visit interaction will be the model covariates. When performing these analyses in the baseline blood eosinophils ≥ 0.3 Giga/L population, the baseline eosinophil level will be removed from the model covariates. Ethnicity will be included as the covariate only in the models for spirometry parameters, specifically. Differences in LS means, the corresponding 95% CI and the p-value will be provided for comparison between dupilumab and placebo along with descriptive statistics.

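### The SAP sends the additional PROs to the Week 12 % predicted FEV1 model: PACQLQ and PRQLQ-IA keep one visit, EQ-5D-Y none, contradicting the protocol and the SAP's own Week 52 model

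*SAP*

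**What the plan says.** SAP 2.4.4.5.1 covers the additional PROs from the list in 2.1.3.5. It states that change from baseline "will be analyzed using the same MMRM model for the key secondary endpoint analysis" described in 2.4.4.2.1, in the Type 2 and eosinophils ≥0.3 Giga/L populations. LS mean differences, confidence intervals and p-values are promised, along with descriptive statistics.

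The model in 2.4.4.2.1 takes "change from baseline in % predicted FEV₁ values up to Week 12 as response variables, and treatment, baseline weight, region, ethnicity" and further terms. The sample SAS code selects Visits 3 to 8 ("avisitn le 8 and ittfl='Y"). Age is absent from both. SAP Table 3 explains: "The model covariates are updated by removing age, sex, and baseline height", because these effects "have already been accounted in the predicted FEV1 calculation equation".

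Two other places give a different plan:

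- SAP 2.4.4.3.1: in the same two populations, "change from baseline for other continuous endpoints at all time-points will be analyzed using MMRM model including measurements up to Week 52". Age is a covariate, and ethnicity enters only for spirometry parameters.
- Protocol 11.4.5: "Patient reported outcome variables collected in this study include the ACQ-IA questionnaire" ACQ-7 score, PAQLQ(S)-IA, PACQLQ and PRQLQ-IA. The MMRM covariates include age, and dupilumab is compared with placebo at every timepoint.

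EQ-5D-Y is in the SAP list (2.1.3.5.5) but not in protocol 11.4.5. The SAP notes its two parts: "The EQ-5D-Y consists of 2 pages, the EQ-5D-Y descriptive system and the EQ visual analogue scale".

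**The concern.** A model built for Week 12 lung function has been assigned to questionnaires with a different schedule. PACQLQ and PRQLQ-IA are first measured after baseline at Week 12, the last visit that the model admits. EQ-5D-Y is first measured after baseline at Week 24, beyond its limit.

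The covariates do not carry over either. Age was removed because the reference equation for predicted FEV1 already contains it. No such equation stands behind a quality-of-life score.

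At stake is whether the SAP fixes one analysis for these instruments. A programmer following 2.4.4.5.1 and one following 2.4.4.3.1 would produce different tables: different visits, different covariates and, for EQ-5D-Y, a model against none.

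**Working it through.** No sample size or power figure is involved. The check is to cross each instrument's schedule with the model's time limit and then compare the texts.

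**Inputs**

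- Model limit: Week 12 (SAP 2.4.4.2.1 text; SAS code, Visits 3 to 8).
- PACQLQ and PRQLQ-IA, post-baseline: Weeks 12, 24, 36, 52 and 64 (protocol flow chart; protocol 11.4.2).
- EQ-5D-Y, post-baseline: Weeks 24, 52 and 64 (protocol flow chart; the Visit 8 list in 10.1.8 omits it, the Visit 14 list in 10.1.11 includes it).

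**Count of scheduled post-baseline visits**

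| Instrument | Up to Week 12 | Up to Week 52 | Including Week 64 | Share used by the assigned model |
|---|---|---|---|---|
| PACQLQ | 1 (Week 12) | 4 (12, 24, 36, 52) | 5 | 1 of 4, or 1 of 5 |
| PRQLQ-IA | 1 (Week 12) | 4 (12, 24, 36, 52) | 5 | 1 of 4, or 1 of 5 |
| EQ-5D-Y | 0 | 2 (24, 52) | 3 | 0 of 2, or 0 of 3 |

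For comparison, % predicted FEV1 has 6 visits up to Week 12 (Weeks 2, 4, 6, 8, 10 and 12), which is what the model was written for.

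**Consequence for the fit.** With a single visit, the visit, treatment-by-visit and baseline-by-visit terms are redundant, so the PACQLQ and PRQLQ-IA model reduces to an ANCOVA at Week 12. With no visit, the EQ-5D-Y model cannot be fitted.

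**Could early discontinuation visits supply EQ-5D-Y data?** No. SAP Table 13 assigns every post-baseline EQ-5D-Y record up to day 266 to Visit 14 (Week 24). A questionnaire completed on day 43 or day 85 is therefore labelled Week 24 and still falls outside the limit.

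**Texts side by side**

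| Item | SAP 2.4.4.5.1 via 2.4.4.2.1 | SAP 2.4.4.3.1 | Protocol 11.4.5 (PACQLQ, PRQLQ-IA) |
|---|---|---|---|
| Visits | Up to Week 12 | All timepoints up to Week 52 | Each timepoint |
| Age | Omitted in text and code | Included | Included |
| Ethnicity | Included | Spirometry only | Not listed |

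SAP Table 7, which summarises the same key secondary model, still lists age, sex and baseline height. So 2.4.4.2.1 is not consistent about age. Table 7 leaves the Week 12 limit in place.

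**Declared changes.** SAP Tables 2 and 3 record the covariate change for % predicted FEV1 only. Neither mentions PACQLQ, PRQLQ-IA or EQ-5D-Y.

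**Likely origin (inference).** Protocol 11.4.5 also says that PROs are handled in the manner of % predicted FEV1, and the FEV1 model in protocol 11.4.2.2.1 includes age and data up to Week 52. (Protocol 11.4.2.4 speaks of data up to Week 12 for the key secondary endpoint, so the protocol is not uniform here.) The SAP kept the pointer to FEV1 but narrowed that model, and the PROs inherited the narrowing.

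**The case against.** The best counter-argument is that the SAP, read as a whole, plans all visits. The Week 52 model in 2.4.4.3.1 covers other continuous endpoints in the same two populations. SAP 2.1.3.5 files all these instruments under a heading that calls them secondary, so a rule in the secondary-endpoint section can reach them. Appendix M lists PROs and continuous endpoints at all time points for those populations, and Table 13 defines windows at every collection visit. On this view 2.4.4.5.1 borrows only the type of model. Strict literalism would also import % predicted FEV1 as response and baseline, which nobody intends.

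Much of this stands. It makes an all-visit analysis the probable intention. But it confirms the conflict rather than removing it: 2.4.4.5.1 is the rule specific to the additional PROs, and it names a section with a stated time limit.

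A reader might infer that EQ-5D-Y has no post-baseline data, or that the PRO objective can no longer be answered. The documents support neither. EQ-5D-Y is collected at Weeks 24, 52 and 64, and 2.4.4.5.1 itself plans descriptive statistics. The secondary PRO objective is served by ACQ-IA and PAQLQ(S)-IA; ACQ-7-IA at Week 24 has its own model and its own places in the testing hierarchy. Protocol 9.4.1 classes PACQLQ, PRQLQ-IA and EQ-5D-Y as exploratory, and none appears in SAP Table 9 or 10.

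**Conclusion.** The point holds as a wrong and contradictory cross-reference. Applied literally, the inferential model uses 1 of 4 post-baseline visits up to Week 52 for PACQLQ and PRQLQ-IA and 0 of 2 for EQ-5D-Y. It also carries a covariate set that departs, undeclared, from protocol 11.4.5 for PACQLQ and PRQLQ-IA.

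The practical weight is limited. The type I error plan, the primary and key secondary analyses and the data collection are untouched. No effect of omitting age on the randomised comparison has been shown; the objection is that the stated reason does not apply to a questionnaire.

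Two assumptions underlie this. First, the additional PROs are PACQLQ, PRQLQ-IA and EQ-5D-Y, matching protocol 9.4.1; SAP 2.1.3.5 also lists ACQ-IA and PAQLQ(S)-IA. Second, the cross-reference is taken to include the time limit of the section it names. If it means only the type of model, the visits are recovered, but the SAP still does not say so and the covariates remain unsettled.

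**What to change.** Reword SAP 2.4.4.5.1 as follows:

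- Name the endpoints: PACQLQ, PRQLQ-IA and the EQ-5D-Y VAS.
- Replace the reference to 2.4.4.2.1 with the Week 52 MMRM of 2.4.4.3.1: treatment, age, baseline weight, region, baseline eosinophil, FeNO and ICS dose levels, visit, treatment-by-visit, own baseline and baseline-by-visit. Omit ethnicity. Drop eosinophil level in the ≥0.3 Giga/L population, as 2.4.4.3.1 already does.
- Summarise the five EQ-5D-Y dimensions descriptively. Each has three levels, so a change-from-baseline MMRM does not suit them.
- State that Week 64 is summarised descriptively outside the model, since the Week 52 model excludes it for all three instruments.

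With this, PACQLQ and PRQLQ-IA contribute 4 visits and the EQ-5D-Y VAS contributes 2. The covariate list in Table 7 can be brought into line with 2.4.4.2.1 in the same edit.

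The cost is SAP wording only: no new data, no change to conduct and no alpha consequence.
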